## STUDY GLOSSARY

3MSE	MODIFIED MINI-MENTAL STATUS EXAM
AB	BETA AMYLOID
AD	ALZHEIMER'S DISEASE
ADAS-COG	ALZHEIMER'S DISEASE ASSESSMENT SCALE – COGNITIVE SUBSCALE
ADCS	ALZHEIMER'S DISEASE COOPERATIVE STUDY
ADCS-ADL	ALZHEIMER'S DISEASE COOPERATIVE STUDY - ACTIVITIES OF DAILY LIVING
ADEAR	ALZHEIMER'S DISEASE EDUCATION AND REFERRAL CENTER
ADNI	ALZHEIMER'S DISEASE NEUROIMAGING INITIATIVE
AE	ADVERSE EVENT
AMCI	AMNESTIC MILD COGNITIVE IMPAIRMENT
ANCOVA	ANALYSIS OF COVARIANCE
APOE/APOE4	APOLIPOPROTEIN (APOE) EPSILON 4 (APOE4)
BDNF	BRAIN-DERIVED NEUROTROPHIC FACTOR
BID   BID	BIS IN DIE (TWICE A DAY)
BUN	BLOOD UREA NITROGEN
CDR-SB	CLINICAL DEMENTIA RATING – SUM OF BOXES
CFR	CODE OF FEDERAL REGULATIONS
CMRGLC	CEREBRAL METABOLIC RATE OF GLUCOSE UTILIZATION
CNS	CENTRAL NERVOUS SYSTEM
CPD	CONTROLLED PARTICLE DISPERSION
CPK	CREATINE PHOSPHOKINASE
CREB	CAMP RESPONSE ELEMENT-BINDING PROTEIN
CRF/E-CRF	CASE REPORT FORM/ELECTRONIC CASE REPORT FORM
CSF	CEREBRAL SPINAL FLUID
DNA	DEOXYRIBONUCLEIC ACID
DSMB	DATA & SAFETY MONITORING BOARD
DSM-IV	DIAGNOSTIC AND STATISTICAL MANUAL OF MENTAL DISORDERS, FOURTH EDITION
DSRS	DEMENTIA SEVERITY RATING SCALE
EAG	ESTIMATED AVERAGE GLUCOSE
ECG	ELECTROCARDIOGRAM
EDC	ELECTRONIC DATA CAPTURE

EDTA	ETHYLENE DIAMINE TETRA ACETIC ACID
ELISA	ENZYME-LINKED IMMUNOSORBENT ASSAY
EMPA	EMPAGLIFLOZIN
FCSRT	FREE AND CUED SELECTIVE REMINDING TEST
FDA	FOOD AND DRUG ADMINISTRATION
FDG PET	FLUORO DEOXY GLUCOSE POSITRON EMISSION TOMOGRAPHY
GCP	GOOD CLINICAL PRACTICE
GEE	GENERALIZED ESTIMATING EQUATION
GGT	GAMMA GLUTAMYL TRANSPEPTIDASE
GSK3B	GLYCOGEN SYNTHASE KINASE 3 BETA
HGA1C	HEMOGLOBIN A1C
HC	HOMOCYSTEINE
HCT	HEMATOCRIT
HCY	HOMOCYSTEINE
HEENT	HEAD   EARS   EYES   NOSE   THROAT
HGB	HEMOGLOBIN
HIPAA	HEALTH INSURANCE PORTABILITY AND ACCOUNTABILITY ACT
HOMA-IR	HOMEOSTATIS MODEL ASSESSMENT OF INSULIN RESISTANCE
ICF	INFORMED CONSENT FORM
ICH	INTERNATIONAL CONFERENCE ON HARMONISATION
IDE	INSULIN DEGRADING ENZYME
IGF-1	INSULIN-LIKE GROWTH FACTOR-1
INI	INTRANASAL INSULIN
IRB	INSTITUTIONAL REVIEW BOARD
ITT	INTENT-TO-TREAT
LDH	LACTATE DEHYDROGENASE
LP	LUMBAR PUNCTURE
LTP	LONG TERM POTENTIATION
MCV	MEAN CORPUSCULAR VOLUME
ML	MILLILITER
MMA	METHYLMALONIC ACID
MMSE	MINI MENTAL STATE EXAMINATION
MPRAGE	MAGNETIZATION PREPARED RAPID GRADIENT ECHO
MR/MRI	MAGNETIC RESONANCE / MAGNETIC RESONANCE IMAGING

NBAC	NATIONAL BIOETHICS ADVISORY COMMISSION
NIA	NATIONAL INSTITUTE ON AGING
NIH	NATIONAL INSTITUTES OF HEALTH
NINCDS/ADRDA	NATIONAL INSTITUTE OF NEUROLOGICAL AND COMMUNICATIVE DISEASES AND STROKE / ALZHEIMER'S DISEASE AND RELATED DISORDERS ASSOCIATION
NBDA	N-METHYL – D-ASPARTATE
NSAID	NON-STEROIDAL ANTI-INFLAMMATORY DRUGS
OHRP	OFFICE FOR HUMAN RESEARCH PROTECTIONS
PBMC	PERIPHERAL BLOOD MONONUCLEAR CELL
PD	PROJECT DIRECTOR
PCP	PRIMARY CARE PHYSICIAN
PET	POSITRON EMISSION TOMOGRAPHY
PHI	PROTECTED HEALTH INFORMATION
PI	PRINCIPAL INVESTIGATOR
PID	PARTICIPANT ID
RBC	RED BLOOD CELL
RE	RANDOM EFFECTS
ROI	REGIONS OF INTEREST
SAE	SEVERE ADVERSE EVENT
SD	STANDARD DEVIATION
SGOT	SERUM GLUTAMIC OXALOACETIC TRANSAMINASE
SGPT	SERUM GLUTAMIC PYRUVIC TRANSAMINASE
T	TESLA
TSH	THYROID STIMULATING HORMONE
U/A	URINALYSIS
WBC	WHITE BLOOD COUNT

TITLE	Study of Nasal Insulin to Fight Forgetfulness "SNIFF" – Combination Intranasal Insulin and Empagliflozin Trial
PROJECT DIRECTOR	[name].
STUDY SPONSOR	Wake Forest University Health Sciences (WFUHS) / Alzheimer's Disease Research Center (ADRC)
STUDY PHASE	Phase II Pilot Study
INDICATION	Preclinical AD, amnestic mild cognitive impairment (aMCI) or mild Alzheimer's disease (AD)
AIM OF STUDY	The proposed pilot study will provide safety and efficacy preliminary data regarding singular and combined effects of two therapeutic approaches, intranasal insulin and treatment with the sodium-glucose cotransporter type 2 inhibitor (SGLT2i) empagliflozin, to correct bioenergetic and vascular dysfunction in adults with preclinical AD and amnestic mild cognitive impairment (aMCI) or early AD
PRIMARY OBJECTIVE	We will test the hypothesis that 1 month of treatment with INI (40 IU q.i.d.), with the SGLT2i empagliflozin (empa; 10 mg q.d.), and with combined insulin plus empagliflozin (INI+empa) will result in safety profiles (number of treatment-related serious adverse events/primary outcome) that are similar to placebo.
SECONDARY OBJECTIVES	We will determine the effects of singular and combined therapy on AD cerebrospinal fluid biomarkers, cerebral blood flow (CBF) and cognition.
PRIMARY OUTCOME MEASURE	Number of treatment-related serious adverse events
SECONDARY OUTCOME MEASURES	PACC5, ADAS-Cog14, CSF A $\beta$ 40, A $\beta$ 42, total tau, and phospho-tau 181, whole brain CBF
STUDY DESIGN	Single-site, double-blind study
SAMPLE SIZE	n=60
SUMMARY OF KEY ELIGIBILITY CRITERIA	
 
Cognitively normal with positive amyloid (amyloid PET SUVR>1.21, CSF A<math>\beta</math>42<600 pg/ml)
 
Diagnosis of amnestic mild cognitive impairment (MCI) or early AD (CDR 0.5 or 1, MMSE>21)
 
Age: 55 to 85 years (inclusive)
 

DRUG DOSAGE & FORMULATION	40 International Units Humulin® R U-100 (Eli Lilly, Inc.) q.i.d.; empagliflozin (10 mg q.d.)
DURATION OF PARTICIPATION	8 weeks (4 weeks on active treatment)
PLACEBO	Insulin diluent (Eli Lilly, Inc.); cellulose capsule

ROUTE OF ADMINISTRATION	Intranasal (insulin); oral (empagliflozin)
PROCEDURES	Physical and neurological exam, nasal examination, cognitive testing, magnetic resonance imaging (MRI), continuous glucose monitoring, actigraphic sleep assessment, lumbar puncture, vitals, clinical labs, CSF and blood analysis and banking and APOE genotyping.

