### 3.8 Safety and Compliance

No treatment-related serious adverse events (SAEs) occurred during the study; most adverse events (AEs) were minor, such as mild rhinitis. AEs with an occurrence of >5% in any group are listed in Table 3. The total AE mean was higher for the low dose group compared with placebo (low dose mean total AEs with standard error=1.44±0.20, placebo =0.80±.22, p=0.04), with a similar trend for the high dose and placebo group comparison (high dose mean total AEs =1.21±0.16, placebo =0.80±.22, p=0.10). Mean compliance (number of completed doses) ranged from 95-97% and did not differ across groups.

**Table 3 | Total number of adverse events and percent of sample for all events occurring for at least 5% of the participants in any treatment group.**

	Placebo	Low Insulin	High Insulin
Total AEs	27/56.7%	55* /72.2%	51+ /68.4%
Dizziness	3/10%	3/8.3%	5/13.2%
Headache	1/3.3%	4/8.3%	2/5.3%
Nose bleed	0/0.0%	6/8.3%	3/2.6%
Rhinitis	1/3.3%	8/16.7%	4/7.9%
URI	2/6.7%	2/5.6%	1/2.6%
Fall	2/6.7%	1/2.8%	1/2.6%
Rash	2/6.7%	1/2.8%	2/2.6%
Other	16/46.7%	30/58.3%	33/60.5%

\* Low Insulin Total AEs > Placebo, p<0.05

+High Insulin Total AEs > Placebo, p<0.10

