### **5.2 Rationale for Primary and Secondary Outcome Measures**

Because no published study has examined the safety of empagliflozin in adults with Alzheimer's disease or in combination with intranasal insulin, the proposed study specifies safety, defined as number of treatment-related adverse events, as the primary outcome..

Regarding secondary measures, in previous studies intranasal insulin acutely improved cognitive performance and affected CSF levels of AD biomarkers as well as MRI measures of vascular integrity (Reger et al. 2008; Craft et al. 2012; Kellar et al. 2021). Thus examining effects on these measures will provide information to be used in the design of a future Phase II trial.

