## **6.0 STUDY OVERVIEW**

The study will consist of a single site, randomized, double-blind trial comparing the effects of 4 weeks of INI (40 International Units q.i.d.), empa (10 mg q.d.) and combined INI and empa compared with placebo on CSF biomarkers and cognition. At study entry, participants will be randomized to one of 4 conditions: INI, empa, INI+empa, placebo. Participants who are cognitively normal but have abnormal elevations of brain amyloid (n=20) or who have MCI or early AD (n=40) will be enrolled. The primary outcome measure will consist of safety (treatment-related serious adverse events). Secondary measures will consist of CSF biomarkers, cognition, and cerebral blood flow. Exploratory measures will include continuous glucose levels and sleep quality as assessed with actigraphy.

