### **17.2 Reporting SAEs**

Any serious and adverse event due to any cause, which occurs during the course of the investigation (i.e. any time after informed consent, regardless of study drug exposure), will be reported to the PI and study physician within 24 hours of learning of the event. All serious adverse events will be reported to the Wake Forest IRB within 7 days of study personnel learning of the event.

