### **20.4 Data and Safety Monitoring Plan**

The principal investigator and study clinician(s) will be responsible for the overall monitoring of the data and safety of study participants, with assistance by members of the study staff. Participants will be screened at the beginning of the study and will be monitored carefully at each study visit. Participants will be queried for serious adverse events (SAEs) and selected AEs (those temporally related to study procedures) at each study visit. All SAEs and selected AEs will be recorded on an AE case report form. Based on the nature of the AE, study clinicians will determine the severity of the event and association with the study. All serious adverse events will be reported. Serious adverse events are defined as events that are (1) life-threatening or fatal, (2) result in severe or permanent disability, or (3) require hospitalization. SAEs will be reported to the IRB within 7 days of investigator

knowledge of the event if they are related and unanticipated (i.e. if they qualify as an unanticipated problem). All serious adverse events will be followed until resolution, or 90 days after study participation has been terminated.

"Severity" of events will be graded according to the following guidelines:

1. Mild: The participant is aware of, but can easily tolerate, the event
2. Moderate: The discomfort of the event is severe enough to interfere with some usual activities
3. Severe: The participant is incapacitated, and unable to perform most or all usual activities

The "study-relatedness" will be assigned according to the following guidelines:

1. Definitely Related: The reaction follows a reasonable temporal sequence and is known to be an effect of participation or a procedure
2. Possibly Related: The reaction follows a reasonable temporal sequence, and current medical knowledge does not preclude a relationship between participation or procedure and the event.
3. Unlikely: Little evidence to suggest a causal relationship (e.g. the event did not occur within a reasonable time after administration of the trial medication) or another reasonable explanation for the event (e.g. another clinical condition or other concomitant treatment).
4. Definitely Unrelated: Current medical knowledge precludes a causal relationship between participation or procedure and the event or the cause of the reaction is known to be other than participation or procedure.

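### The primary safety comparison counts only SAEs judged treatment-related, so an unexpected drug-caused SAE can be left out of the comparison with placebo

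*Combined protocol and SAP*

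**What the plan says.** - **Outcome.** The synopsis names the "number of treatment-related serious adverse events" as the primary outcome and hypothesises "safety profiles (number of treatment-related serious adverse events/primary outcome) that are similar to placebo". Sections 1.1, 6.0 and 12.0 use the same filtered count. Section 5.2 keeps the filter but omits seriousness: "safety, defined as number of treatment-related adverse events, as the primary outcome".
- **Analysis.** Section 12.0 submits that count to a repeated measures analysis of variance. The other analyses it lists concern diagnostic status, biomarkers, cognition and cerebral blood flow. It plans no by-arm comparison of SAEs of any cause.
- **Attribution.** In Section 20.4 study clinicians assign one of four grades, from *Definitely Related* to *Definitely Unrelated*. The grades are framed mainly around taking part in the study or a study procedure, whereas Section 16.1 asks about causal relation to the study drug. *Unlikely* covers "Little evidence to suggest a causal relationship" or a reasonable alternative cause. No section says which grades make an event treatment-related.
- **Capture.** Section 17.2 sends to the PI and study physician within 24 hours "Any serious and adverse event due to any cause, which occurs during the course of the investigation". Section 20.4 puts every SAE on a case report form.
- **Design.** There are 60 participants in four equally allocated arms, one of them placebo (synopsis; Section 15.2, Randomization). Site assessors are blinded (Section 15.3).
- **Prior knowledge.** Section 5.2 states that "no published study has examined the safety of empagliflozin in adults with Alzheimer's disease or in combination with intranasal insulin". Section 13.2 (combined insulin and empagliflozin) does describe ketoacidosis in a subset of Type 2 diabetic patients, and hypoglycemia, when insulin is given with this drug class.

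**The concern.** In a randomised trial with a concurrent placebo arm, comparing the arms already addresses whether treatment causes SAEs. A case-by-case causality judgement ahead of that comparison can remove drug-caused events as well as background ones. The judgement draws on existing knowledge, and that is thinnest for empagliflozin in Alzheimer's disease and for empagliflozin with intranasal insulin.

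The hypothesis is that the active arms resemble placebo. If genuine drug-caused SAEs are graded unrelated, an active arm's count moves down towards placebo, which is the direction of the desired conclusion. Blinding helps to keep attribution even-handed between arms, but it does not bring back events that were excluded.

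**Working it through.** **Step 1. Follow one event through the plan.** Take an unexpected SAE that is drug-caused, in a participant with another illness.

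- Section 17.2: it is recorded and reported whatever its cause.
- Section 20.4: with reasonable timing, and nothing known that rules out a link, it fits *Possibly Related*. If the clinician sees the other illness as a reasonable explanation, it also fits *Unlikely*. The scale does not say which prevails.
- Section 12.0: it enters the comparison only if its grade counts as treatment-related, and that cut-off is not given.
- If it is not counted there, no other planned analysis compares it by arm.

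So the event can be excluded from the comparison, though it is not lost from the record.

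**Step 2. Inputs.** There is no stated figure to reproduce: Section 12.1 says no power calculation was done, and no SAE rate, margin or alpha is given. Arm size is 60/4 = 15. Assumed: risk p of a drug-caused SAE of 5%, 10% or 20%; share k of those events graded related of 100%, 75%, 50% or 25%.

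**Step 3. Chance that an arm shows at least one counted drug-caused event.** The formula is 1 − (1 − pk)^15. For p = 0.10 and k = 0.5 it gives 1 − 0.95^15 = 0.537.

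| p | k = 100% | 75% | 50% | 25% |
|---|---|---|---|---|
| 5% | 54% | 44% | 32% | 17% |
| 10% | 79% | 69% | 54% | 32% |
| 20% | 96% | 91% | 79% | 54% |

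The k = 100% column has no background events, so it is not the all-cause endpoint. With an assumed background risk b, the all-cause chance is 1 − (1 − p − b)^15. At p = 10% this is 83%, 85% and 91% for b = 1%, 2% and 5%. Background alone gives 14%, 26% and 54%, so part of that is noise.

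**Step 4. Combination against placebo, with background noise.** Assume b = 5% and p = 10%, acting independently, 15 per arm. The chance that one arm has more affected participants is found by summing the products of the two binomial probabilities.

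| Endpoint | Risk, combination | Risk, placebo | Combination higher | Placebo higher |
|---|---|---|---|---|
| All-cause | 1 − 0.95 × 0.90 = 0.145 | 0.05 | 72% | 10% |
| Filter keeps 75% of drug events, 10% of background | 1 − 0.925 × 0.995 = 0.080 | 0.005 | 68% | 2% |
| Filter keeps 50% of drug events, 10% of background | 1 − 0.95 × 0.995 = 0.055 | 0.005 | 54% | 3% |

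**Step 5. What neither endpoint can do.** No events in 15 leaves a one-sided 95% upper bound of 1 − 0.05^(1/15) = 18.1%. A two-sided Fisher test at an assumed 0.05 needs 5 against 0 (p = 0.042); 4 against 0 gives p = 0.0996. At a 20% excess with 2% background, power is about 17% for all-cause SAEs. Under the filter, with no background events, it is 16%, 6%, 1% and below 0.1% for k = 100%, 75%, 50% and 25%. At a 10% excess it is 3% or less either way.

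**The case against.** The related-SAE endpoint is stated consistently in the synopsis and Sections 1.1, 6.0 and 12.0. Attribution is made in a double-blind trial, and every SAE still reaches the PI and study physician. *Possibly Related* is broad: what is unknown cannot rule out a link, and reasonable timing is easily met with daily dosing. The filter also removes background noise. In Step 4, keeping 75% of drug events leaves the chance of seeing the excess at 68% against 72%, with fewer reversals (2% against 10%). Every rate used is an assumption.

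Most of this stands, and it limits the point. Some stronger readings are tempting but not supported:

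- *Unexpected harm is removed before the arms are compared.* The scale permits exclusion. It does not show that exclusion will usually happen, nor that harms already listed will be kept preferentially.
- *Nothing is known about the combination.* Section 5.2 speaks of published studies of empagliflozin in Alzheimer's disease or with intranasal insulin. Section 13.2 lists risks of insulin with this drug class.
- *The pilot shows that counting events rather than people distorts the SAE result.* Table 3 in Section 3.8 gives low-dose ratios to placebo of (55/36)/(27/30) = 1.70 for events and 72.2/56.7 = 1.27 for participants. These are adverse events of all kinds, described there as mostly minor, and say little about repeat SAEs over four weeks.

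What the objection does not answer is the gap itself: an undefined cut-off, and no by-arm analysis in which an excluded SAE would appear.

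**Conclusion.** The point holds as a gap in the planned comparison. The only between-arm safety analysis depends on a clinical causality grade with no stated cut-off, so an unexpected drug-caused SAE can be left out of it while remaining on record. Such a loss pulls an active arm towards placebo, and it matters most for empagliflozin with intranasal insulin.

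The size is not determined by the documents. At an assumed 10% drug-caused risk and 15 per arm, the chance of counting at least one such event falls from 79% to 54% if half are graded unrelated, and to 32% if three quarters are. If clinicians recognise nearly all drug-caused SAEs, the loss is small and the filter even reduces noise. A reader might infer that an all-cause endpoint would let the trial establish similarity to placebo. It would not, because precision at about 15 per arm is too low under either definition.

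**What to change.** In the synopsis and Sections 1.1 and 12.0, add a named between-arm safety comparison, either as the primary analysis or as a key analysis alongside it: the number and percentage of participants with at least one SAE of any cause, from first dose of study drug to end of follow-up, by randomised arm, with the difference from placebo and an exact 95% interval. Keep treatment-related SAEs and event totals as supporting summaries. State which Section 20.4 grades count as treatment-related, and whether relatedness means to the study drug (Section 16.1) or to participation and procedures (Section 20.4). Reconcile Section 5.2, which omits seriousness, with the other sections.

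The cost is wording only, since Sections 17.2 and 20.4 already capture every SAE. The price is some background events, which add noise but are balanced across arms in expectation. The intervals will be wide and should be reported as such, not read as evidence of similarity.

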## 1.0 INTRODUCTION

An urgent need exists to find effective treatments for AD that can arrest or reverse the disease at its earliest stages. The emotional and financial burden of AD to patients, family members, and society is enormous, and is predicted to grow exponentially as the median population age increases. Current FDA-approved therapies are modestly effective at best. The proposed study will examine singular and combined effects of two novel therapeutic approaches to correct bioenergetic and vascular dysfunction in adults with amnestic mild cognitive impairment (aMCI). Metabolic and vascular disorders are well-known risk factors for Alzheimer's disease (AD); although the mechanisms through which they influence risk is not completely understood, accruing research has identified numerous potential contributors, including insulin resistance, bioenergetic defects, inflammation, impaired vascular function, and reduced clearance of protein aggregates, all of which have cumulative adverse effects on brain function with aging. Based on this evidence, it has been suggested that medications used to treat metabolic and vascular function could be repurposed as therapies for AD.

Sodium-glucose co-transporter-2 inhibitors (SGLT2is) belong to a new class of agents that has attracted considerable interest because of concomitant effects on metabolism and vascular function in adults with Type 2 diabetes and/or cardiovascular disease. In the periphery, SGLT2is reduce hyperglycemia through off-loading of glucose into urine, and modulate sodium handling leading to reduced blood pressure and improved cardiovascular function. They have been tested in numerous large trials and shown to be safe; because they do not increase insulin, they can be administered without risk of hypoglycemia in non-diabetic adults. SGLT2 has been identified in brain, as well as in choroid plexus epithelial cells where it may play a role in cerebrospinal fluid (CSF) production and brain glymphatics. SGLT2 expression in brain is increased with traumatic brain injury and cerebral ischemia. Preclinical studies indicate effects of SGLTis in the brain that are of relevance to AD, including a shift from glycolysis to fatty acid metabolism, thereby providing an alternative energy substrate, enhanced mitochondrial function, decreased oxidative stress, and inhibition of the mTOR signaling pathway. In an AD mouse model, the SGLT2 inhibitor empagliflozin reduced amyloid plaques, inflammation, and microhemorrhages, while enhancing performance on memory measures.

Another approach to correcting brain metabolic and vascular dysregulation in AD involves direct provision of insulin to the brain via intranasal insulin (INI) administration using devices specialized for nose-to-brain delivery. In pilot and Phase II trials this approach improved cerebral glucose utilization, AD CSF biomarker profiles, white matter hyperintensity volume progression, and cognition. Although a recent Phase II trial showed improvement with only one of two devices, in subsequent pilot studies we have determined that this failure may have been due in part to different methods of delivery used by the two devices, requiring different dosing strategies, and have validated a dosing protocol that verifies reliable delivery of insulin to the CNS.

SGLT2is and insulin exert beneficial metabolic and vascular effects in brain through different mechanisms. SGLT2i effects are not directly related to insulin, although through promoting a switch to fatty acid metabolism, peripheral hyperinsulinemia is reduced with corresponding decrease in insulin resistance. In contrast, insulin likely works directly through its receptors which are prolific throughout brain to promote synaptic viability, neurogenesis, and vasoreactivity, with downstream amelioration of amyloid and tau pathology. Thus, although each approach could be predicted to benefit AD symptoms and pathology, it is possible that additive or synergistic effects would be observed by combining the

two approaches. In large trials, insulin and SGLT2is have been co-administered with no adverse events. Further, because intranasal insulin does not lower blood glucose, and SGLT2is lower blood glucose only in the presence of hyperglycemia, and are not associated with hypoglycemia, the combined regimen is likely to be safe. This hypothesis will be tested in the proposed proof of concept study which will examine whether the safety profiles of 4 weeks of combined and singular administration of intranasal insulin and empagliflozin compared with placebo. We will also examine effects of treatment on cognition, CSF biomarkers, and cerebral perfusion. If successful, information gained from the study will inform the design of a future Phase II trial.

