### **10.6 Continuous Glucose Monitoring**

The Abbott Freestyle Libre Pro is a continuous glucose monitor (CGM) system; a thin filament sensor the size of a quarter covered with a waterproof patch will be placed by a clinician or qualified study team member on the back of the participant's upper arm and worn for 7 days, then removed by the participant. The sensor records and uploads glucose data every 15 min. A report of average glucose

levels and number of hyperglycemic/hypoglycemic episodes can be linked to events such as meals, sleep, and activity. Participants will be assessed over a 1-week period.

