### **13.2 Safety of combined insulin and empagliflozin**

Combined therapy of insulin and SGLT2is, including empa, was associated with rare but increased risk of ketoacidosis in the subset of Type 2 diabetic patients who have reduced insulin secretory capacity. Hypoglycemia has also been noted with combined administration, thought to be due to reduced hyperglycemia and related improvement in insulin sensitivity without concomitant reduction in insulin dosing. The proposed study will exclude participants with Type 2 diabetes, and will monitor blood glucose at all visits, as well as with continuous glucose monitoring during the last week of treatment. No other adverse interactions have been noted and SGLT2is are commonly prescribed for insulin-treated diabetics because of the multiple benefits on glycemic control and vascular function (Scheen, *Nature*, 2020).

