## **16.0 ADVERSE EVENTS**

### **16.1 Definition**

An adverse event (AE) is defined as per the Code of Federal Regulation Title 21 Part 312.

<http://www.accessdata.fda.gov/scripts/cdrh/cfdocs/cfcfr/cfrsearch.cfm?fr=312.32>

Adverse events which occur after informed consent is signed include but are not limited to: (1) worsening or change in nature, severity, or frequency of conditions or symptoms present at the start of the study; (2) participant deterioration due to primary illness; (3) intercurrent illness; and (4) drug interaction. An abnormal laboratory value will only be reported as an AE if the investigator considers it to be an AE, or if it leads to the participant being withdrawn from the study.

The investigator should attempt to establish a diagnosis of the event based on signs, symptoms, and or other clinical information. In such cases, the diagnosis should be documented as the AE and not the individual signs or symptoms. Symptoms and conditions present at the beginning of the study will be characterized, so that AEs can be defined as any new symptom, or any increase in frequency or severity of an existing symptom.

Following questioning and evaluation, all AEs, whether determined to be related or unrelated to the study drug by a medically qualified site PI or clinician (MD, DO, NP or PA), must be documented in the participant's medical records, in accordance with the investigator's normal clinical practice, and on the AE e-CRF. Each AE is evaluated for duration, severity, seriousness, and causal relationship to the study drug.

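### The Introduction's claim of no adverse events with insulin plus SGLT2 inhibitors conflicts with section 13.2, and the statistical plan has no summary of non-serious or sensor-detected hypoglycemia by arm

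*Combined protocol and SAP*

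**What the plan says.** **On past experience with the combination.** Section 1.0 states "In large trials, insulin and SGLT2is have been co-administered with no adverse events". The next sentence argues that intranasal insulin leaves blood glucose unchanged and that SGLT2 inhibitors "are not associated with hypoglycemia, the combined regimen is likely to be safe". Section 13.2 on combined therapy says that the pairing "was associated with rare but increased risk of ketoacidosis in the subset of Type 2 diabetic patients" (those with reduced capacity to secrete insulin) and that "Hypoglycemia has also been noted with combined administration". It attributes the hypoglycemia to insulin doses that were not lowered as glycemia improved. As safeguards it says "The proposed study will exclude participants with Type 2 diabetes, and will monitor blood glucose at all visits", and it adds CGM in the final week of treatment.

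**On what counts as safety.** The synopsis and sections 1.1, 6.0 and 12.0 make the primary outcome the number of treatment-related serious adverse events. Section 5.2 makes it treatment-related adverse events, without the restriction to serious ones. Section 20.4 calls an event serious if it is fatal or life-threatening, causes severe or permanent disability, or needs hospitalization.

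**On recording.** Sections 10.1 and 16.1 have all AEs documented, but section 16.1 adds that "An abnormal laboratory value will only be reported as an AE if the investigator considers it to be an AE" or if it leads to withdrawal. Section 20.4 asks only for SAEs and a selected group of AEs linked in time to study procedures.

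**On glucose monitoring.** Section 6.0: "Exploratory measures will include continuous glucose levels and sleep quality as assessed with actigraphy". Section 10.6 describes a report in which average glucose and the "number of hyperglycemic/hypoglycemic episodes can be linked to events such as meals, sleep, and activity". No glucose cut-off is given. Section 12.0 names no glucose or hypoglycemia analysis, and the synopsis lists no glucose outcome.

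**The concern.** The trial is to test whether the combination, never studied in this population, is as safe as placebo. The protocol's own risk section names hypoglycemia as something seen with combined use, and it points to CGM as part of the answer. The Introduction tells its reader that there is nothing of the kind to look for. The outcome list and the statistical plan then follow the Introduction, not the risk section: they contain no glucose result.

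If the plan were followed as written in section 12.0, the combination arm could show more low-glucose episodes on the sensor than the other arms, and the safety conclusion could still rest on an SAE count of zero. Whoever designs the next trial would not learn from the stated safety result that the sensor data pointed the other way.

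**Working it through.** **1. The two accounts side by side.** The Introduction's sentence is about past large trials and carries no qualifier. Section 13.2 describes past use of the same drug classes together and reports two kinds of adverse event. Excluding diabetes from this trial bears on whether those events will recur here. It does not make the historical statement true, so one of the two texts has to change.

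**2. Where a non-serious hypoglycemic event would go.** Take the case in section 13.1: one participant on intranasal insulin with 52 mg/dl after a missed meal and hard exercise, described as mild.
- Synopsis and sections 1.1, 6.0, 12.0: not counted unless it met a seriousness criterion. Nothing reported about the case meets one of the three in section 20.4.
- Section 5.2: counted, if judged treatment-related.
- Sections 10.1 and 16.1: recorded if it is an AE. A laboratory value alone depends on the investigator's view or on withdrawal.
- Section 20.4: recorded only if serious or linked in time to a study procedure.

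The same event is therefore in or out of the data, and in or out of the primary outcome, according to which section is followed.

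**3. How much the sensor adds.** Section 13.2 promises blood glucose at every visit. Table 4 shows blood draws at visits 1, 3 and 6 only, and the lists for visits 4 and 5 (sections 8.4, 8.6) name no glucose test. Between dispensing of drug at visit 3 and the last visit, the only glucose measurement in the schedule is the second CGM week. The first CGM week runs from visit 2 to visit 3, before study drug is handed out (sections 8.2, 8.3). The second runs from visit 5 to visit 6 (sections 8.6, 8.7). Those visits are labelled post-treatment, but section 13.2 places this CGM in the last week of treatment, and vials and pills are collected at visit 6. A within-person comparison is thus available once the timing is stated plainly.

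**4. What an SAE count can show.** The plan gives no power, alpha, margin or event rate to reproduce; the only design figures are 20 + 40 = 60 participants and equal allocation to four arms, so 60/4 = 15 per arm. Exact upper limits for zero events in 15:
- one-sided 95%: 1 − 0.05^(1/15) = 0.181
- two-sided 95%: 1 − 0.025^(1/15) = 0.218

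Zero counts are plausible. Preliminary study 1 had no treatment-related SAE among 36 + 38 = 74 insulin-treated participants (sections 3.2, 3.8), although at 20 or 40 IU a day, with another device and without empagliflozin.

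**5. Illustration under assumed rates.** None of these rates is in the documents. Let h be the chance that a combination-arm participant has hypoglycemia and s the share of cases that are serious and judged related. Chance of at least one case in 15: 1 − (1 − h)^15. Chance that at least one enters the SAE count: 1 − (1 − hs)^15.

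| h | any case | counted, s = 0 | s = 10% | s = 20% |
|---|---|---|---|---|
| 5% | 53.7% | 0 | 7.2% | 14.0% |
| 10% | 79.4% | 0 | 14.0% | 26.1% |
| 20% | 96.5% | 0 | 26.1% | 45.8% |

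Over this range the SAE count would usually miss hypoglycemia that was present.

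**6. What a by-arm summary can show.** Against 0 of 15 on placebo, 4 of 15 affected gives a two-sided Fisher p of 0.100 and 5 of 15 gives 0.042. Only a large difference would reach significance, so the summary is descriptive.

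**The case against.** Several points for the plan are sound, and they limit what can be claimed.

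- A reader might infer that the combination caused ketoacidosis and hypoglycemia. Section 13.2 does not say that: it reports an association and an observation. It confines ketoacidosis to a diabetic subset and ties hypoglycemia to unreduced insulin dosing. Section 6.4 excludes diabetes and regular use of insulin or other anti-diabetic drugs within two months of screening.
- A reader might infer that the plan's rules shut hypoglycemia out of the safety result. No such rule exists. A serious, related hypoglycemic event enters the primary count, a non-serious related one would enter under section 5.2, and section 16.1 has all AEs recorded and assessed for severity and cause.
- A reader might extend the laboratory-value clause in section 16.1 to sensor readings. The text does not clearly cover CGM, which has its own section apart from clinical laboratory tests, and symptomatic hypoglycemia could be an AE in its own right.
- The Introduction's expectation of safety does not hang on the faulty sentence alone. It is drawn in a separate sentence about how each drug affects glucose, and section 13.1 supports the insulin part with several studies and one mild exception.
- In an unpowered proof-of-concept study, placing CGM among exploratory measures is a legitimate choice, and exploratory results can still be reported.

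What remains is the conflict between sections 1.0 and 13.2, the two primary-outcome definitions, the two recording rules, and the absence from section 12.0 of any analysis of the measurement that section 13.2 relies on.

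**Conclusion.** The concern holds in a limited form. The Introduction's unqualified sentence is inconsistent with section 13.2. Non-serious hypoglycemia is outside the outcome that section 12.0 analyses, its recording depends on which section is followed, and CGM hypoglycemia has neither a cut-off nor a planned safety analysis. The documents do not support the stronger claims that the combination is known to cause these events in people like those enrolled, or that hypoglycemia is barred from the safety result.

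The size of the gap cannot be stated, because no hypoglycemia rate is given; the rates in the table are assumptions. What can be stated is that 15 per arm with no SAEs leaves a true SAE rate of up to 18.1% (one-sided) or 21.8% (two-sided) unexcluded, assuming equal arms and no dropout. That is a general limit of the sample size and does not measure hypoglycemia. It does mean that the SAE count should not be the only support for the safety conclusion when a relevant measurement is already being taken. The change is a cheap improvement; the gap does not invalidate the design.

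**What to change.** 1. Reconcile the Introduction's sentence on past co-administration with section 13.2.
2. State one primary-outcome definition, so that section 5.2 agrees with the synopsis and sections 1.1, 6.0 and 12.0.
3. State one AE recording rule, so that sections 16.1 and 20.4 agree.
4. In the synopsis and sections 6.0 and 12.0, name CGM hypoglycemic episodes as a supporting safety outcome. Report by arm the number of participants affected, with exact confidence intervals, and the episode counts. Compare the end-of-treatment sensor week with each participant's own pre-treatment week, using a glucose cut-off chosen by the study team and fixed before unblinding.
5. Say in sections 8.6 and 8.7 that the second sensor week falls on treatment, as section 13.2 has it, and reconcile section 13.2's promise of glucose at all visits with Table 4.
6. Have the safety conclusion cite the CGM result beside the SAE count.

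Cost: text changes only for the outcome itself, since both sensor placements and the episode report are already planned. Item 5 needs the study team to confirm the timing. The downside is one more safety result, possibly less favourable than the SAE count, and descriptive only at about 15 per arm.
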